#### Sample size estimates

 $\alpha$  (two-sided) = 0.05, power (1- $\beta$ ) = 0.90 A previous study revealed that hypothermia incidence is 39.9%[2]. The control and warming group is 1:1. According to our preresearch Warming effect size = 0.36, 10% drop-out, 793 patients are required in total.

# Data safety and monitoring

Because the study is a small trial with interventions likely to be safe, an experienced anesthesiologist and an orthopedist who are not involved in the study will monitor the safety and the trial procedures. They meet at the trial design period, prior to start of recruitment (review the study protocol), and every 3 months after start of the recruitment.

The members of the DSMB should review recruitment, randomization, adherence to blinding, potential complications of epidural puncture, data accuracy and integrity.

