#### Methods

# Overview of design

This is a randomized, single-blinded, multi-center study clinical trial to determine both clinical outcomes of stratified warm strategy to prevent intraoperative hypothermia. Patients enrolled into this trial will be from elective major surgery population in PUMC Hospital, Beijing Hospital and Xuanwu Hospital from April 1, 2019 to March 31, 2021. We plan to enroll approximately 800 patients. We review the medical records and have a face-to-face interview to determine whether the patient is eligible for the study according to the inclusion and exclusion criteria. Hypothermia risk will be estimated through PREDICTOR model in all eligible patients. According to hypothermia risk level, these patients will be stratefied into high, moderate and low risk group. Patients in each group will be randomly categorize into warm group and control group. For controll group traditional passive warm was used, which means cotton blanket was used to prevent hypothermia. While, for active warm group, different warm strategy are used according to risk level, prewarm for 30min only for low risk patients, prewarm 30 min and fluid warm for moderate risk patients, prewarm and forced-air warm throughout operation and fluid warm for high risk patients. Temperature will be record though the operation. All participants were followed up every day after surgery until 6 month after operations. Any post operation complication will be recorded carefully.

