#### Measurements

Intervention: traditional cotton blanket warm vs. active warm according to risk level

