#### Plans for randomization and blinding

Randomization: Patients will be randomized using stratified blocked randomization. The random treatment assignments are placed in sealed, numbered, and opaque envelops who will not be involved in opening them. Two staffs signed and recorded the next unopened envelope before opening the envelope. Investigators will access the allocation about an hour before surgery is expected to start, after consent is obtained. Allocation will thus be remained concealed until the last practical moment.

Blinding: Patients are all blind to the allocation.

Reduce confounding factor: Patients in GA group were given 1.5-2mg/kg Propofol, 0.8mg/kg rocuronium, 2ug/kg fentanyl for induction of anesthesia. After tracheal intubation, anesthesia was continued with sevoflurane in 50% nitrous oxide with oxygen, and end-tidal anesthesia gas is maintained 0.9-1.2 MAC. Supplemental fentanyl doses of 50ug are administered for blood pressure elevation or heart rate increases amounting to more than 10% of baseline.

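### The safety monitors' itemised charge names complications of epidural puncture, which is in neither arm, and names no harm of the warming under test

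*Combined protocol and SAP*

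**What the plan says.** The Data safety and monitoring section appoints an anesthesiologist and an orthopedist "who are not involved in the study will monitor the safety and the trial procedures". They meet during the design period, before recruitment starts, and every 3 months once it has started. The section justifies this light arrangement by calling the trial small and its interventions likely to be safe. It then itemises the charge: "The members of the DSMB should review recruitment, randomization, adherence to blinding, potential complications of epidural puncture, data accuracy and integrity".

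The interventions are set out elsewhere. Under Measurements the comparison is "traditional cotton blanket warm vs. active warm according to risk level". Overview of design gives the control arm as passive warming: "For controll group traditional passive warm was used, which means cotton blanket was used to prevent hypothermia". The active arm depends on the risk stratum: "prewarm for 30min only for low risk patients, prewarm 30 min and fluid warm for moderate risk patients", and "prewarm and forced-air warm throughout operation and fluid warm for high risk patients".

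The only anaesthetic regimen is in Plans for randomization and blinding, in a paragraph that begins "Patients in GA group were given" and goes on to describe induction, tracheal intubation and inhaled maintenance. Overview of design also says that temperature is recorded through the operation and that postoperative complications of any kind are recorded, with follow-up to 6 months.

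**The concern.** The itemised sentence is an instruction to the monitors, not background, and it is the only place where the plan says what they should look at. Its one patient harm belongs to a procedure that the plan describes nowhere. The harms that the randomised treatment could plausibly cause, such as skin thermal injury, overheating, or faults in a warming device or fluid warmer, are not mentioned.

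What is at stake is the interim safety review. Monitors who work from the list would ask for epidural events at each three-monthly meeting, and nothing in the list would prompt a summary by arm of events related to warming. The plan rests its light monitoring on the expectation that warming is safe, so the charge should be able to test that expectation. As itemised, it does not.

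**Working it through.** No sample size, power or event count bears on this point, and the plan gives no figure to reproduce. The check is a comparison of texts.

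**Step 1. What the charge contains, item by item.**

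| Item in the charge | Kind | Linked to warming or to the control arm? |
|---|---|---|
| Recruitment | Conduct | No |
| Randomization | Conduct | No |
| Adherence to blinding | Conduct | No |
| Complications of epidural puncture | Patient harm | No |
| Data accuracy and integrity | Data quality | No |

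Only one item is a patient harm.

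**Step 2. Is epidural puncture part of the trial as described?** The word *epidural* occurs once in the available text, in the charge itself. The control arm is a cotton blanket. The active arm is prewarming, with fluid warming added for moderate risk, and fluid warming plus forced-air warming for high risk. The anaesthetic described is general anaesthesia. Epidural puncture is therefore in neither arm and not in the described anaesthetic.

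**Step 3. Is a harm of warming named anywhere?** None appears in the charge, in Outcome variables or in the Analysis plan.

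**Step 4. What do the general provisions cover?**

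| Provision | Covers | Leaves open |
|---|---|---|
| General mandate to monitor safety (Data safety and monitoring) | Safety oversight in general terms | Names no event; the itemised sentence that makes it specific points to epidural puncture |
| Recording of postoperative complications (Overview of design) | A burn noticed after surgery, for example | Not routed to the monitors or requested by arm; faults before or during surgery may fall outside it |
| Temperature recording (Overview of design) | Overheating and hypothermia would show in the data | Not routed to the monitors |
| Hypothermia as primary outcome; surgical site infection and adverse cardiovascular events as secondary outcomes (Outcome variables) | Collected, with between-group tests in the Analysis plan | Not named for review during the trial |

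The gap that remains is one of naming and routing. Warming-related events are not specified, and neither they nor the relevant trial outcomes are listed for the monitors.

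The check covers the available text only. One part of the document and one figure could not be seen.

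**The case against.** The strongest reply is that the plan already provides cover. The monitors have a general safety mandate, any postoperative complication is recorded, temperatures are recorded throughout surgery, and hypothermia, infection and cardiovascular events are outcomes with planned tests. This stands, and it rules out several stronger readings that a reader might infer:

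- *Safety oversight is absent.* It is not; the general mandate exists.
- *The control arm's main harm is missing from the outcomes.* Hypothermia incidence is the primary outcome, although no severity grade is given.
- *The trial could report nothing on warming injury.* Some injuries could be captured as postoperative complications. What is missing is a specified collection that covers the whole period of warming.

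A second reply is that epidurals may be used as an adjunct in major surgery. The documents do not exclude this, so it cannot be said that an epidural event could never arise in a trial patient. Even then, the charge would still omit the harms of the randomised treatment, and the sections would still describe different things.

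A third reply concerns where the wording came from. The reference to a GA group matches no randomised group, and an orthopedist monitors a trial in elective major surgery generally. One might infer that text was carried over from another protocol. That is possible, but *GA group* may simply mean patients who receive general anaesthesia. The mismatch is a fact; its cause is not established, and the point does not depend on it.

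**Conclusion.** The point holds in a limited form. The itemised charge names one patient harm, and that harm is in neither arm and not in the anaesthetic described. It names no harm of the interventions under test. The general provisions reduce the gap but do not close it.

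This is a clear internal mismatch in safety oversight that should be corrected. It does not affect the primary comparison or its analysis.

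No numerical magnitude is claimed. It is tempting to take half of the planned 793 patients, about 397, and work out how likely a rare warming injury would be to appear. The documents do not support that calculation. They give no injury rate, and the 793 already includes a 10% allowance for drop-out. Forced-air warming throughout surgery is confined to the high-risk stratum, and fluid warming to the moderate- and high-risk strata, and stratum sizes are not stated.

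The conclusion assumes that the part and the figure that could not be seen do not describe an epidural technique or a fuller monitoring charge.

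**What to change.** In Data safety and monitoring, replace the epidural item with review by arm of:

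- warming-related adverse events: skin thermal injury, overheating, and faults of a warming device or fluid warmer;
- hypothermia, surgical site infection and adverse cardiovascular events, which the trial already collects.

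State that the warming-related events are recorded before, during and after surgery, so that they do not depend on being classed as postoperative complications. The case report form is not among the documents; if it already has these fields, only the routing to the monitors needs to be added.

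If neuraxial techniques are in fact used, reconcile Overview of design, Plans for randomization and blinding, and Data safety and monitoring so that they describe the same trial.

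The cost is one sentence and, at most, a few data fields, with minor extra data collection. The monitors and their meeting schedule stay as they are. This is a list of events to review; it proposes no treatment rule.
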